5.6 Data Analysis

Aims 1 and 2 - Sample Size:

Sample size and power calculations are based on our primary outcome, occurrence of reproductive planning discussion between patient and provider with shared decision making (SDM), and rely on formulas specified for use in cluster randomized trials accounting for non-use of the tool in the intervention group and attrition.[39] We estimate that the baseline prevalence of discussions of contraception and/or preconception health among women who could potentially become pregnant will be 50%, based on estimates from the nationally-representative VA ECUUN study and our pilot study.[2] Based on field testing, we estimate that 30% of women participants enrolled in the intervention arm who receive the text with the MyPath link will not actually view the tool and the sample size calculation will thus account for this estimated non-use. Assuming a kappa coefficient of 0.01 and attrition of 5%, a sample of 456 patients (approximately 15 patients for each of 30 providers) will yield 80% power in 2-sided tests with a type-1 error rate of 5% to detect a 20-percentage point increase in reproductive planning with SDM to 70%. This difference is clinically meaningful and consistent with what we observed in our pilot (22% increase).

Aims 1 and 2 - Missing data and subject dropouts:

For the 3- and 6-month follow-up periods, we assume 20% attrition (15% lost to follow up and 5% who either become pregnant or change to desiring pregnancy). This is a conservative estimate based on 7% attrition at 3-months in our pilot. All appropriate efforts will be made to avoid missing data, including monitoring of missingness and subject dropout rates by the PI and study manager or research coordinator biweekly during the study data collection phase. The research coordinator will investigate causes and remedies. For key analysis variables that have 15% or more missing values, we will analyze factors that are associated with having a missing value and perform a sensitivity analysis using multiple imputation to allow an unbiased analysis for all subjects.

Because informative missingness would violate the covariate-dependent missing at random (CDMAR) assumption of the standard multiple imputation procedure, we will conduct sensitivity analyses in which we multiply impute missing data under plausible informative missing data mechanisms – in particular, lower contraceptive continuation rates among participants with missing values of this outcome, in one or both arms. In all analyses, we will check for departures from model assumptions.

Aims 1 and 2 - Outcome Analyses:

Intention to Treat: Primary analyses of treatment effects will be intent-to-treat, with participants analyzed in the groups to which they were originally assigned irrespective of whether or not they received the intervention. Therefore, participants who “cross-over” from their assigned study arm will be analyzed in their originally assigned group. Participants will be withdrawn/removed from the study and excluded from analysis after enrollment in either of these circumstances:

- Participants who do not attend their scheduled visit with the study provider after enrollment (and thus have an undefined outcome for patient-provider reproductive planning discussion).
- Participants who find out they are pregnant during their enrollment visit (and thus would have been ineligible had this been known prior to enrollment).

Secondary analysis will utilize causal inference methods (e.g., using instrumental variables) to estimate the treatment effect between participants who actually used the MyPath tool vs. those who did not (i.e., accounting for adherence).

Analytic Subgroups: Certain secondary outcomes will be analyzed only among a pre-defined cohort/subgroup of participants. Assignment to these groups is made at patient screening/enrollment (pre-intervention). Definitions of the full sample and analytic subgroups are as follows:

- **The full sample:** includes all individuals who are eligible for and enrolled in the study based on inclusion/exclusion criteria (capable of pregnancy with no prior history of hysterectomy, oophorectomy, sterilization, not currently pregnant, interested in receiving information about either pregnancy planning or birth control, and able to receive VA text messages).
- **At risk of unintended pregnancy (UIP):** a subgroup of the full sample defined as having had sex with a man in the past 12 months who has not had a vasectomy and not currently seeking pregnancy. Outcomes related to contraception will be assessed in the subgroup at risk for UIP.
- **Considering pregnancy:** a subgroup of the full sample who are considering or ambivalent about pregnancy in the next few years. The exploratory preconception health behaviors outcomes will be assessed in this subgroup.

Description of the study populations: Provider, patient, and clinic leader participants will be described through summary statistics of demographic characteristics, and for providers, practice characteristics.

Aim 1 Primary Outcome: The analysis for our primary outcome of patient-provider discussion of reproductive planning with share decision making (SDM) will be assessed post-visit in **the full sample**. For our Aim 1 primary outcome analysis, we will use a mixed effects logistic regression model to test whether the odds of occurrence of reproductive planning with SDM is significantly different in the intervention versus control arm post-visit. In addition to estimating the odds ratio, we will also estimate the difference in predicted probabilities between the intervention and control group.

Covariates to be included in adjustment models are as follows:

- Study site (categorical)
- Clinic practice-type (binary) – Women’s Clinic Y/N
- Visit Type (virtual/telephone vs. in-person)
- Patient Age (categorical)
- Patient Race/ethnicity (categorical)
- Patient Household Income (categorical)
- Patient Marital Status (categorical)
- Patient Parity (categorical)
- Mental Health Diagnosis (one or more, binary)
- Medical Comorbidity (one or more, binary)

Aim 1 Secondary Outcomes: Secondary outcomes for Aim 1 will be assessed post-visit.

Secondary outcomes assessed **in the full sample** include provider-patient communication self-efficacy and reproductive planning knowledge. Secondary outcomes assessed **in the subgroup at risk of UIP** include contraceptive decisional conflict, values concordance, and contraceptive method decision. We will use a mixed effects logistic regression model to test whether these outcomes are different in the intervention versus control arm post-visit.

Aim 2 Secondary Outcomes: Secondary outcomes for Aim 2, including continuous contraceptive use, consistent contraceptive use, and unintended pregnancy, will be assessed at 3- and 6-month follow up **in the subgroup at risk of UIP**. We will use a mixed effects logistic regression model to test whether outcomes differ between groups. For continuous and consistent contraceptive use outcomes, we will adjust for self-reported pre-study contraceptive use (measured at the post-visit survey).

Exploratory Preconception Health Behaviors: These outcomes will be assessed among a subgroup of study participants considering pregnancy in the next few years or who are ambivalent about pregnancy (unsure). Preconception risk factors will be measured at baseline and using medical record data, and behaviors to modify those risk factors will be assessed at post-visit, 3-months, and 6-months.

Exploratory Analyses of Interaction Effects: **For Aim 1 and 2 outcomes**, we will assess modification of the effect of assignment to the intervention by the following 4 pre-specified factors: age, race/ethnicity, visit modality (in-person or virtual) and clinic type (Women’s Health Clinic yes/no). We will assess evidence for effect modification by adding the effect modifier and its interaction with the treatment assignment indicator to the primary analysis models specified above.

Exploratory Analyses of Patient-Centered Contraceptive Outcomes: Recognizing that pregnancy intentions may fluctuate and participants in the subgroup at risk of UIP may decide that they wish to pursue pregnancy during the study timeframe, we will create “goals-concordant” measures for both continuous contraceptive use over 6 months and consistent contraceptive use at 6 months. Goals-concordant continuous contraceptive use will be defined as non-continuous use among women who desire pregnancy now; any continuous use outcome among women who are not trying but would be okay with pregnancy; and continuous use among women who desire pregnancy later, never, or who are not sure. Goals-concordant

consistent contraceptive use will be defined as no method or inconsistent use among women who desire pregnancy now; no method, inconsistent use or consistent use among women who are not trying but would be okay with pregnancy; and consistent contraceptive use among women who desire pregnancy later, never, or who are not sure.

In addition, we will create a “goals-concordant” reproductive behaviors outcome at 6 months, combining consistent contraceptive use and folic acid supplementation. Goals-concordant reproductive behavior will be defined as taking folic acid among women who desire pregnancy now; taking folic acid or consistent contraceptive use among women who are not trying but would be okay with pregnancy or who are unsure; and consistent contraceptive use among women who desire pregnancy later or never.

Aim 3 – Analysis Plan

Quantitative analyses will involve both MyPath analytics data and estimated cost data and will provide summary statistics such as total cost estimates, means or medians (e.g., of time spent using the tool), and proportions (e.g., of participants who used the tool, or who used specific components of the tool), etc. These analyses will be descriptive.

The qualitative interviews will be recorded, transcribed, and analyzed. Transcripts will be analyzed using inductive and deductive content analysis, which will allow us to obtain specific information about implementation barriers and facilitators as well as capture unanticipated themes and previously unidentified factors[41]. We will (1) deductively develop *a priori* codes based on the specified RE-AIM domains in Table 8, and (2) inductively create emergent codes to capture data that do not fit *a priori* codes. Two trained coders will independently code all transcripts. For each group separately (Veterans, providers, clinic leaders), we will begin with an initial codebook using our *a priori* codes and then add codes as they emerge[42, 43]. To maintain the iterative process even as the final codebooks are applied, open codes will continue to be developed and added to the codebooks. Transcripts coded before addition of the new codes will be reexamined with the updated codebooks to ensure consistency. All analyses will be facilitated by use of ATLAS.ti software. Code output will be reviewed and discussed amongst the investigator team to identify common themes within and across groups.

Staff Analysis Responsibilities and Involvement:

The PI/SC and study biostatisticians are responsible for overseeing the analysis of all Aim 1 and 2 outcomes. The VA-employed study data analyst will be responsible for carrying out Aim 1 and 2 analyses in VA computing space, using STATA, SAS or R software packages. The PI/SC and Qualitative Methodologist are responsible for overseeing the analysis of all Aim 3 qualitative interviews. The PI/SC, study manager, research coordinator, and qualitative methodologist will be involved in the Aim 3 qualitative data analysis, including coding and synthesis of qualitative findings. Qualitative analysis will be facilitated by Atlas.ti software housed in VA computing space.

Co-I and Collaborator involvement: Study co-investigators will collaborate with the Puget Sound team to do analysis for the study. Co-Is will be involved to inform high-level analysis planning and preparation of findings for publication or presentation. Non-LSI Co-Is, including [name] and [name] will have access to de-identified data only, and will not have access to any participant PHI.

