The Centers for Disease Control and Prevention (CDC)[17] and other national organizations[18, 19] recommend routine delivery of reproductive planning services in primary care to improve reproductive decision making and outcomes. Reproductive planning services include assessment of women's childbearing desires and goals followed by individualized contraceptive and/or preconception counseling to address women's goals and needs[17]. Beyond advocating for increased delivery of reproductive planning services, national organizations also emphasize the importance of patient-centeredness in reproductive planning counseling and care[17, 18]. A

key component of patient-centered counseling is shared decision making (SDM), a two-way process of communication between patients and providers that incorporates patients' goals, values and preferences into the decision making process[20, 21]. SDM in contraceptive counseling is preferred by women[22-24], including Veterans[25], and is associated with increased rates of contraceptive continuation and use of effective contraceptive methods[26-28].

Delivery of patient-centered reproductive planning services happens infrequently in primary care outside[29, 30] or within VA[2]. As the vast majority of basic reproductive healthcare in VA is provided in primary care rather than specialist gynecology care[31], provision of reproductive planning counseling and services by VA primary care providers is essential. In a large national survey, however, only 38% of Veterans at risk of pregnancy reported discussing contraception and/or preconception health with their primary care provider in the past year[2]. Of additional concern, studies indicate that key elements of patient-centered counseling, such as active listening and eliciting women's values and preferences, are often absent in reproductive planning encounters in VA[25, 26, 32]. Patient-level barriers to high-quality reproductive planning counseling identified in qualitative work by [name] include women Veterans' perceived low self-efficacy to request this counseling and perceived lack of time in visits. Veterans' low self-efficacy is linked to negative past experiences of reproductive health counseling in the military and VA, including gender-based discrimination and dismissal of reproductive health concerns, resulting in fears that reproductive planning conversations will not be valued by VA providers[25].

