Quantitative: Quantitative data collection to assess reach will include intervention adherence by patient participants (i.e., the proportion of patients in the intervention arm who used the intervention). Analytic data from the software developers hosting MyPath will be obtained. Analytic data will verify self-reported use of the tool, quantify time spent using the tool, and describe which pages of MyPath are most visited to better understand the reach of MyPath among women receiving the intervention. Women in the intervention group will be assigned a personal code consisting of two words and a number when they access MyPath, and MyPath analytic data will be linked to this code. Linkage of the code will be maintained in a crosswalk behind the VA firewall. Lastly, process data will be collected to estimate costs of implementing the intervention, including time spent training intervention arm providers, costs of disseminating the tool, and costs of software

Study Population

Providers: We will enroll up to 100 primary care providers who have seen at least 30 unique reproductive-aged women in the past year. Providers will be recruited across the 9-16 study sites. Trainees who must staff with attending providers (e.g. residents and medical students) will be excluded from participation. After patient recruitment is complete, we will invite intervention arm providers to complete qualitative interviews for Aim 3 about their experiences seeing patients who used the tool.

Patients: We anticipate enrolling approximately 456 women Veteran patients (not to exceed 570 patients) scheduled to see enrolled providers over the course of 18 months of recruitment. We aim to recruit approximately 15 patients scheduled to see each study provider, for a cluster size of 15 and a total sample size of 456, though depending on enrollment rates and in efforts to balance the number of patients in study arms, additional patients may be enrolled up to a maximum of 570. Up to 30 intervention arm Veteran participants will be interviewed for Aim 3. They will be purposively sampled for variety in characteristics such as intervention adherence, race/ethnicity, age, parity, provider in a women's clinic vs non-women's clinic, and site/geographic location.

Clinic Leaders: We will enroll and interview up to 20 clinic leaders who work with enrolled providers for Aim 3.

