5.2 Recruitment Methods

Sample Size

Providers: Up to 100 providers will be enrolled for Aims 1 and 2, and all intervention arm providers (up to approximately 38) will be invited to complete the qualitative interview at the end of the patient recruitment/enrollment phase.

Patients: no more than 570 patients will be enrolled for the RCT, and up to 30 intervention-arm patients will complete the qualitative interview after the post-visit survey.

Clinic Leaders: Up to 35 clinic leaders will complete qualitative interviews at the end of the patient recruitment/enrollment phase.

Identifying and Recruiting Study Participants

Providers: Providers from each study site will be identified as potentially eligible for study recruitment using data available through CDW. These data will be accessed by our data requisitioner using the VA Informatics and Computing Infrastructure (VINCI). Recruitment emails will be sent to potentially eligible providers by study staff (see attached email, Attachment F). Recruitment emails will include a study information statement for providers (Attachment G) and will instruct providers to respond if they do not wish to be contacted about participation in the study. Opt-out responses from providers will be collated by the study manager. Recruitment lists will be made available to study RAs at least one week later. RAs will contact providers by telephone, email, and MS Teams messenger. Screening, consent, and study enrollment will occur over the telephone (see attached script, Attachment H). No more than 3 voice messages, 3 emails, and 3 MS Teams direct/instant messages will be sent by study staff to potentially eligible providers that have not opted-out of study contact.

Patients: After study providers have been enrolled, the data requisitioner will pull lists of all potentially eligible VA patients (women ages 18-44 without medical record evidence of infertility) empaneled to enrolled providers. Recruitment letters will be mailed to these patients (Attachment I) by the study manager or research coordinator at the start of the study.

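### Does the power paragraph rest on the wrong control rate, the wrong effect and an inconsistent number of providers?

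*Combined protocol and SAP*

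**What the plan says.** All the inputs are in section 5.6, under the sample size for Aims 1 and 2. The calculation is said to be for the primary outcome, discussion with SDM. The baseline sentence reads: "We estimate that the baseline prevalence of discussions of contraception and/or preconception health among women who could potentially become pregnant will be 50" per cent, credited to a national VA survey and the pilot. The claim is 80% power, two-sided 5%, "to detect a 20-percentage point increase in reproductive planning with SDM to 70" per cent. The paragraph also gives a kappa of 0.01, 5% attrition, and 30% of intervention-arm women not viewing the tool, which it says the calculation allows for.

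Three other places bear on it:

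- Section 2.0 reports that "only 38% of Veterans at risk of pregnancy reported discussing contraception and/or preconception health with their primary care provider in the past year", citing the reference used for the 50%. It adds that key elements of patient-centered counseling "are often absent in reproductive planning encounters in VA".
- Section 5.6, Outcome Analyses: "Primary analyses of treatment effects will be intent-to-treat".
- Section 5.1 plans about 15 patients per provider, "for a cluster size of 15 and a total sample size of 456". Section 5.2 allows up to 100 providers, refers to "all intervention arm providers (up to approximately 38"), and says "no more than 570 patients will be enrolled for the RCT".

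**The concern.** Three things catch the eye.

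First, discussion with SDM is a subset of discussion, so its rate cannot be higher. If 50% is the rate of any discussion, the true control rate for the primary outcome may be lower, and the Introduction gives a reason to expect that. The effect might shrink with it. The pilot's 22% increase, cited in support, is not tied to a named outcome. The 38% and the 50% share a reference, and the step between them is not explained.

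Second, the primary analysis keeps women who never open the link. A 20-point effect in users is then diluted. If 20 points were meant as the intention-to-treat difference, the non-use allowance would be superfluous. If it is the user effect, calling it the detectable difference could mislead someone reading the primary result.

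Third, 30 providers at 15 each does not sit easily with 38 per arm or 100 in all. The design effect depends on cluster size.

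This is the plan's only power statement, so if its inputs were wrong, the 80% would be unsupported.

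**Working it through.** **Inputs (section 5.6).** Control 50%, intervention 70%, two-sided 5%, power 80%, kappa 0.01, 15 per provider, non-use 30%, attrition 5%. Allocation is 1:1 (section 5.1).

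**Reproducing 456.** Two-proportion formula, pooled variance under the null and unpooled under the alternative:

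n = [1.960·√(2·0.60·0.40) + 0.842·√(0.50·0.50 + 0.70·0.30)]² / 0.20² = 93.0 per arm

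- Both arms: 2 × 93.0 = 186.0
- Non-use: 186.0 / (1 − 0.30)² = 379.6
- Design effect 1 + (15 − 1) × 0.01 = 1.14: 379.6 × 1.14 = 432.7
- Attrition: 432.7 / 0.95 = 455.5, rounded up to 456

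Without the non-use step the total is 223. The exact match shows how the plan uses its figures: 20 points is the effect in users, and non-use is allowed for as stated.

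**The intention-to-treat contrast.** With 70% use, 0.70 × 20 = 14 points, or 50% against 64%. The effective number per arm is 456 × 0.95 / 2 / 1.14 = 190.

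| Intention-to-treat contrast | Power at 456 |
|---|---|
| 50% v 64% | 78.9% |
| 50% v 64.2% | 80% |
| 50% v 70% | 98% |

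Sizing directly on 50% v 64% gives 468, so the shortcut 1/0.7² costs about one point of power.

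**Sensitivity to the control rate.** Holding the difference at 14 points, 190 per arm:

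| Control rate | Power |
|---|---|
| 20% | 87.0% |
| 25% | 83.6% |
| 30% | 80.9% |
| 38% | 78.5% |
| 45% | 78.2% |
| 50% | 78.9% |

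Moving from 50% to 38% costs 0.4 of a point.

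**Sensitivity to how the effect carries over to SDM.** The documents give no share of discussions that include SDM, so every row below is an assumption. Intervention rate = 0.3 × control rate + 0.7 × rate in users.

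| Assumption | Control v intervention | Power at 456 |
|---|---|---|
| SDM in 90% of discussions, both arms | 45.0% v 57.6% | 69% |
| 80%, both arms | 40.0% v 51.2% | 59% |
| 70%, both arms | 35.0% v 44.8% | 50% |
| 90%, and 95% in users | 45.0% v 60.1% | 84% |
| 80%, and 85% in users | 40.0% v 53.7% | 76% |
| 70%, and 75% in users | 35.0% v 47.3% | 68% |
| 70% with SDM in users as the plan states, control 45% | 45.0% v 62.5% | 93% |
| As above, control 40% | 40.0% v 61.0% | 98.5% |

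**Providers.** 456 / 15 = 30.4, in line with 30. Two arms of 38 give 76. Power for 50% v 64% at kappa 0.01:

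| Providers | 456 patients | 570 patients |
|---|---|---|
| 30 | 78.9% (15.2 each) | 86.0% (19.0 each) |
| 38 | 80.0% (12.0 each) | 87.1% (15.0 each) |
| 76 | 82.2% (6.0 each) | 89.3% (7.5 each) |
| 100 | 82.7% (4.6 each) | 89.8% (5.7 each) |

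Fifteen patients for each of 76 providers would be 1,140, above the cap of 570. But the provider figures are upper limits, and at a given number of patients every step towards them raises power.

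**The case for a change.** The strongest case for a change is that the primary endpoint has no control rate sourced as such. If MyPath produces more discussions but the same proportion of them involve SDM in both arms, the whole contrast shrinks in proportion. Power at 456 would then be 69%, 59% or 50% for shares of 90%, 80% or 70%. Rewording one paragraph is cheap, and it would stop a reader from measuring the primary result against 20 points when the trial was sized for about 14.

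Part of this stands. The baseline sentence does not mention SDM, the step from 38% to 50% is not shown, and 20 points is not labelled as the effect in users.

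The rest is weaker. The paragraph does fix 50% against 70% on the SDM outcome, since a rise of 20 points to 70% leaves no other control rate. The equal-share rows replace the plan's 70% with SDM by a smaller figure. They also assume that a tool meant to promote SDM leaves it unchanged within discussions. Keeping the plan's 70% in users and lowering only the control rate makes 456 conservative. The 38% is for women at risk of pregnancy over a past year. The 50% also draws on the pilot and is for women who could become pregnant, and section 5.4 enrolls only women interested in the topic. These need not be the same quantity. Finally, no section makes 20 points a threshold for success: the primary analysis tests the odds ratio and also estimates a difference in predicted probabilities.

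**Conclusion.** No change to the plan is called for. The sample size is arithmetically sound, and non-use is disclosed and correctly built in. The design has about 79% power for the 14-point intention-to-treat difference that its own inputs imply, and 80% for 14.2 points. This rests on the plan's kappa of 0.01, 5% attrition, 30% non-use, and a 14-point difference that carries over to discussion with SDM. Given that difference, the control rate hardly matters: 78% to 87% over 20% to 50%.

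Whether the effect does carry over cannot be settled from the documents. Reasonable assumptions put power on either side of 80%, so no harm in a known direction is shown. The provider numbers are ceilings and lean the favourable way.

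What remains is missing explanation in a planning paragraph: the source of the 50% as an SDM rate, and the population to which the 20 points applies. A statistician can recover both from the stated inputs, as the exact match to 456 shows. Supplying them would leave the test, the model, the estimand and enrolment as they are.

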
Please complete this survey for “Improving Outcomes for Women Veterans”:
 
[Link to Qualtrics Survey]
 
Questions? Call 206-XXX-XXXX

Reminder: Submit your next survey to help improve women Vets’ healthcare:
 
[Link to Qualtrics Survey]
 
Questions? Call 206-XXX-XXXX

Reminder: Submit survey to support women’s health at VA and receive \$50:
 
[Link to Qualtrics Survey]
 
Questions? Call 206-XXX-XXXX

Please complete VA women’s health study survey by MM/DD to receive \$50:
 
[Link to Qualtrics Survey]
 
Questions? Call 206-XXX-XXXX

Reminder: Help the VA improve care for women Vets and receive \$50:
 
[Link to Qualtrics Survey]
 
Questions? Call 206-XXX-XXXX

All survey questions assessed at each timepoint are provided in the attached Patient Survey Instruments (Attachment Q) and summarized below.

- Baseline survey: Demographics, pregnancy intentions, and whether the patient is at risk of unintended pregnancy (UIP) will be assessed. Baseline preconception health risks will be assessed.
- Post-visit survey: The primary outcome of the occurrence of a reproductive planning discussion with SDM and the secondary outcomes of communication self-efficacy and family planning knowledge will be assessed among all participants. Secondary outcomes relating to contraceptive choices and decisions will also be assessed post-visit among the subgroup at risk of UIP. Whether participants discussed preconception health risks or received any services related to preconception health risks identified at baseline will be assessed among participants considering pregnancy. At the end of the post-visit survey we will ask questions related to use of the intervention for Aim 3, including collecting the users’ assigned personal codes as described above.
- 3- and 6-month surveys: Changes in pregnancy goals and whether the patient continues to be at risk of UIP will be assessed. Secondary outcomes relating to contraceptive use and unintended pregnancy will be assessed among the group remaining at risk of UIP. Preconception health behaviors, an exploratory outcome, will be assessed.

Aim 3 Qualitative Interview: Intervention arm patients who participate in the qualitative interview will be asked questions about their experience receiving the MyPath text message, using or not using the MyPath intervention, and using any other similar health-related tools previously (see interview guide, Attachment S).

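### The Aim 1 contraceptive method decision outcome is not adjusted for pre-study contraceptive use, which is collected in the same survey and adjusted for in Aim 2, so some precision may be lost

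*Combined protocol and SAP*

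**What the plan says.** All references are to the combined protocol and SAP.

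- **Outcome and model (5.6, Aim 1 Secondary Outcomes).** The outcomes in the UIP subgroup "include contraceptive decisional conflict, values concordance, and contraceptive method decision". Their analysis is given in one sentence: "We will use a mixed effects logistic regression model to test whether these outcomes are different in the intervention versus control arm post-visit".
- **Covariates (5.6, Aim 1 Primary Outcome).** The list opens "Covariates to be included in adjustment models are as follows" and has ten items: site, practice type, visit type, age, race/ethnicity, income, marital status, parity, mental health diagnosis and medical comorbidity. The plan does not say whether it also governs the secondary models. Contraceptive use is absent either way.
- **Aim 2 (5.6, Aim 2 Secondary Outcomes).** "For continuous and consistent contraceptive use outcomes, we will adjust for self-reported pre-study contraceptive use (measured at the post-visit survey").
- **Timing (5.5).** The method decision comes from that same survey: "Secondary outcomes relating to contraceptive choices and decisions will also be assessed post-visit among the subgroup at risk of UIP". The summary of the baseline survey does not mention contraceptive use: "Demographics, pregnancy intentions, and whether the patient is at risk of unintended pregnancy (UIP) will be assessed", together with preconception risks.
- **Design.** Section 5.1 randomises providers 1:1, stratified by site and practice type. Section 5.6 sizes the trial on "a sample of 456 patients (approximately 15 patients for each of 30 providers"). Section 5.2 is wider: "Up to 100 providers will be enrolled for Aims 1 and 2", with up to about 38 in the intervention arm.

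**The concern.** A woman's choice of method at a visit plausibly depends on the method she was already using. The plan treats prior use as worth adjusting for when contraceptive use is measured 3 and 6 months later, but not for the contraceptive outcome closest to it in time. It gives no reason for the difference.

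The stratification does not balance prior use, so the arms can differ on it by chance. If prior use predicts the decision, leaving it out makes the comparison less precise than the collected data allow. This happens in a subgroup that is no larger than the sample the trial was sized on.

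**Working it through.** **1. The plan's own figure.** The only sample size stated is for the primary outcome. For 50% v 70%, two-sided 5%, 80% power, pooled variance, 93 per arm are needed, or 186 in total.

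- Non-use of 30%: 186 / 0.70² = 379.6
- Design effect 1 + (15 − 1) × 0.01 = 1.14: 379.6 × 1.14 = 432.7
- Attrition of 5%: 432.7 / 0.95 = 455.5, rounded up to 456

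The figure reproduces, and this point does not touch it. There is no corresponding calculation for the method decision.

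**2. Assumptions for the method decision (none is in the documents).** About 300 women in the UIP subgroup, 30 providers with 10 each, 50% prior use, a between-provider ICC of prior use of 0.01 or 0.05, and a treatment odds ratio of 1.8.

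**3. Chance imbalance in prior use.** SD = √[0.5 × 0.5 × (2/150) × (1 + 9 × ICC)].

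- ICC 0.01: √(0.003333 × 1.09) = 0.060
- ICC 0.05: √(0.003333 × 1.45) = 0.070

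This is 6 to 7 percentage points, and simulation agrees (5.7–7.0). A 6-point imbalance moves the contrast without this covariate by 6 × the difference in decision rate between women with and without prior use: 0.9 points at a difference of 0.15, 2.1 at 0.35 and 3.3 at 0.55.

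**4. Effect of adjustment.** As a guide, the variance is multiplied by about 1 − ρ², where ρ = 0.5 × (difference in decision rate) / √[p(1 − p)] and p is the control mean. For the moderate case ρ = 0.5 × 0.35 / √(0.575 × 0.425) = 0.354, so ρ² = 0.13. The simulation fitted a linear risk-difference model with cluster-robust standard errors (800 replicates, critical value 2.048), with and without prior use. Paired entries are for ICC 0.01 and 0.05.

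| Association | Control decision rate, no prior use v prior use | ρ² | Simulated variance ratio | Power without | Power with |
|---|---|---|---|---|---|
| Weak | 45% v 60% | 0.02 | 0.97, 0.97 | 65.6%, 66.9% | 65.5%, 66.5% |
| Moderate | 40% v 75% | 0.13 | 0.86, 0.83 | 54.0%, 52.6% | 61.4%, 58.1% |
| Strong | 30% v 85% | 0.31 | 0.70, 0.66 | 38.2%, 37.1% | 52.6%, 53.4% |

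Power should be compared within rows only. The odds ratio is held at 1.8, so the true risk difference shrinks down the table. In the moderate row the treated rates are 1.2/2.2 = 0.545 and 5.4/6.4 = 0.844, mean 0.695, against a control mean of 0.575: 12.0 points. The same steps give 0.663 − 0.525 = 13.8 points (weak) and 0.673 − 0.575 = 9.8 points (strong).

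**5. More providers.** With 38 × 2 = 76 providers of 4 women each, the variance ratios are 0.98 (weak), 0.88 (moderate) and 0.68–0.69 (strong). The number of providers makes little difference.

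**Limits.** The simulated providers differ only through prior use, and the comparison model has no other covariates. The Monte Carlo standard error of one power figure is about √(0.5 × 0.5 / 800) = 1.8 points.

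**The case against.** **The outcome's coding is not visible.** The survey items are in an attachment. If the method decision is scored as a change from the current method, prior use is already built in and adjustment may add little. This stands, and the fix is conditional on it.

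**The covariate is not a true baseline.** It is recalled after randomisation, tool use, the visit and the debrief that reveals the topic, in the same sitting as the outcome. Recall that differed by arm would feed into the adjusted contrast. This stands as a caveat. The plan accepts the same risk in Aim 2, and showing the fit without the term makes any dependence visible. A pre-visit measure would be cleaner, but none is described as collected by survey.

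**The ten listed covariates may already absorb part of the gain.** This stands. If the list applies to the secondary models, only the association beyond age, parity, marital status and the rest counts, and that is unknown.

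**Different adjustment sets are not an error in themselves.** Agreed: unintended pregnancy in Aim 2 is not adjusted for prior use either.

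Three stronger readings are tempting, and the documents do not support them.

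- *A reader might infer bias through recruitment, since patients enrol after their provider is randomised.* Section 5.1 keeps research assistants blind to provider arm throughout and to patient arm until the end of the post-visit survey. Section 5.3 withholds the topic from patients until after the visit. What remains is mainly chance imbalance, which the standard error already reflects. Imbalance and lost precision are therefore one point, not two.
- *A reader might infer a 12-point power gain.* With 456 × 0.95 × 0.70 = 303 women, a 50% control rate, a 20 × 0.70 = 14-point effect and ρ = 0.5, power goes from 66% to 79%. The rate and effect belong to the primary outcome, the 70% UIP share and ρ are assumed, and the comparison model has no covariates. At ρ = 0.3 the gain is 4 points. With a 5-point effect, ρ = 0.5 moves power only from 13% to 16%.
- *A reader might infer that adjustment loses no participants.* Section 5.1 lets participants skip any question, so a few may lack the item.

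**Conclusion.** The gap is real and minor. Pre-study contraceptive use is collected and is adjusted for in two related outcomes, but not in the model for the method decision. The consequence is possible loss of precision for one secondary outcome. It is not systematic bias, and the primary analysis and the 456 are unaffected.

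The size cannot be fixed from the documents. Under the stated assumptions the gain runs from nothing useful (weak association) to a variance reduction of about a third (strong), and it may be smaller once the ten listed covariates are in the model. In a logistic model the benefit appears as power and as precision of the difference in predicted probabilities, not as a smaller standard error of the log odds ratio.

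**What to change.** In section 5.6, extend the Aim 2 adjustment sentence so that pre-study contraceptive use is also a covariate for the Aim 1 method decision, unless that outcome is already scored as change from the prior method. In the same place:

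- state how the outcome is coded, and whether the ten-item list applies to the secondary models;
- report the adjusted difference in predicted probabilities, which the plan now specifies only for the primary outcome;
- show the fit without the term as a sensitivity analysis, and say how women who skip the item are handled.

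The cost is a sentence or two and one extra model fit, with no new data. The small downside is reliance on an item recalled after the visit, which assumes recall does not differ by arm, and the loss of a few women who skip it. Settling this before analysis also prevents the adjustment from being chosen once results are known.
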